4.9.3 Laboratory Data

Abnormal laboratory outcomes will be reported. A summary of the number and percentage of patients with abnormal laboratory outcomes will be produced at each visit by treatment group.

Absolute values and change from baseline values for all laboratory assessments will be summarized by descriptive statistics at each visit by treatment group. The baseline for the laboratory, except for the CSF safety lab parameters, will be defined as the last assessment prior to the first lumbar puncture or last assessment on Day 1, whichever occurred first. For the CSF safety lab parameters, the baseline will be defined as the last assessment prior to the first dosing administration or last assessment on Day 1, whichever occurred first.

For the measurement reported as ' $<x$ ' or ' $>x$ ', the value will be set to x .

In addition, the shifts (relative to the normal range) from baseline to the minimum and maximum post-baseline values will be presented. If a subject is missing a baseline value but had a post-baseline value, then the baseline assessment is labeled as

"unknown". Likewise, if a subject had a baseline value but had no post-baseline values, then the minimum and maximum are labeled as "unknown".

The number of patients with abnormal and marked abnormal absolute values for the CSF safety labs, according to the parameter ranges presented in [Table 1](#), will be summarized by treatment and visit.

Table 1 CSF Safety Laboratory Normal Ranges

Parameter	Low	Normal	High	Marked High
Glucose (mmol/L)	<2.2	2.2-3.9	> 3.9	> 4.4
Protein (g/L)	<0.15	0.15-0.5	> 0.5	
Erythrocytes (cells/ μ L)		0	>0	> 5
Leucocytes (cells/ μ L)		0-5	>5	

CSF = cerebrospinal fluid.

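### Replacing a laboratory result of `<x` or `>x` by x can put CSF safety results in the wrong Table 1 category, most clearly for erythrocytes

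*SAP*

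**What the plan says.** The rule is in SAP Version 3, Section 4.9.3 (Laboratory Data). For any measurement reported as `<x` or `>x`, "the value will be set to" x. It exempts no parameter and is not confined to means and other descriptive statistics.

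The same section then uses laboratory values as categories in two displays:

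- Shift tables: "the shifts (relative to the normal range) from baseline to the minimum and maximum post-baseline values will be presented".
- CSF counts by treatment and visit: "The number of patients with abnormal and marked abnormal absolute values for the CSF safety labs, according to the parameter ranges presented in" Table 1.

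Table 1 ("CSF Safety Laboratory Normal Ranges") sets these categories:

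- Glucose (mmol/L): Low below 2.2, Normal 2.2 to 3.9, High above 3.9, Marked High above 4.4.
- Protein (g/L): Low below 0.15, Normal 0.15 to 0.5, High above 0.5.
- Erythrocytes (cells/µL): Normal 0, High above 0, Marked High above 5.
- Leucocytes (cells/µL): Normal 0 to 5, High above 5.

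Nothing in Section 4.9.3 or elsewhere in the Version 3 SAP keeps the `<` or `>` sign when a category is assigned.

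**The concern.** Replacing a censored result by its limit is a common convention for descriptive statistics, where the error is usually small. Classification is different when the cut-points are strict. The limit x is a value that the inequality says the result does not have, and it can lie on the other side of the cut-point from every value the result could have.

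Erythrocytes are the most exposed. Normal is the single value 0, so any positive x moves a `<x` result out of Normal. No coincidence between the reporting limit and a Table 1 limit is needed.

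The drug is given intrathecally, and the SAP treats CSF findings as a safety interest: Section 4.9.2 lists CSF protein and leukocyte events among the selected adverse events. Wrong categories would affect the by-visit counts and also the shift tables. If an erythrocyte baseline of `<1` is stored as 1, the patient starts as High; a real rise to 3 then reads as High to High and the shift from Normal disappears. If some zeros are reported as 0 and others as `<1`, a shift can appear that never happened.

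**Working it through.** The plan gives no figure to reproduce here. The check applies the substitution rule to Table 1 and compares the category it yields with every category the inequality allows.

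**Inputs from the SAP:** the substitution rule and the Table 1 limits, both in Section 4.9.3.

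**Assumed inputs:** the laboratory reporting limits, which the SAP does not give, so a range of x was tried. Cell counts are taken as whole numbers; protein and glucose move in steps of 0.01. For CSF parameters, the normal range in the shift tables is taken to be that of Table 1.

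**Step 1. Erythrocytes reported as `<x`.** After substitution the value is x, which exceeds 0, so the result is High at least.

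| Reported | Set to | Assigned | Possible from the inequality |
|---|---|---|---|
| `<1` | 1 | High | Normal only (count 0) |
| `<2`, `<3`, `<5` | 2, 3, 5 | High | Normal or High |
| `<6` | 6 | Marked High | Normal or High (counts 0 to 5) |
| `<10` | 10 | Marked High | Normal, High or Marked High |

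The assigned category is certainly wrong for `<1` and `<6`. In the other rows it may be right or wrong.

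**Step 2. Results censored exactly at a Table 1 limit.** The value becomes the limit itself, and a strict inequality is not met at its own limit.

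| Parameter | Reported | Assigned | Possible from the inequality |
|---|---|---|---|
| Erythrocytes | `>5` | High | Marked High |
| Leucocytes | `>5` | Normal | High |
| Protein | `<0.15` | Normal | Low |
| Protein | `>0.5` | Normal | High |
| Glucose | `<2.2` | Normal | Low |
| Glucose | `>3.9` | Normal | High or Marked High |
| Glucose | `>4.4` | High | Marked High |

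In every row the assigned category is one that the reported inequality excludes.

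**Step 3. Limits clear of a boundary.** Here the rule gives the right category:

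- Leucocytes `<1`, `<3`, `<5`: Normal. Leucocytes `>100`: High.
- Protein `<0.05`, `<0.10`: Low. Protein `>2`: High.
- Glucose `<1.1`: Low. Glucose `>6`: Marked High.
- Erythrocytes `>1000`: Marked High.

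The errors run both ways: false High or Marked High for erythrocytes reported as `<x`, and missed Low, High or Marked High where the reporting limit equals a Table 1 limit.

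**The case against.** The strongest objection is that the SAP does not show that such results occur. It states no CSF reporting limits and does not say whether a zero cell count is reported as 0 or as `<x`. Table 1 gives normal erythrocytes as 0, which is consistent with zero being a reportable value, though it does not prove it. If zeros are reported as 0, the erythrocyte example never arises. The cases in Step 2 need the reporting limit to coincide with a Table 1 limit; for the `>x` cases, the assay would have to stop quantifying at the normal or marked-abnormal threshold. Nothing in the SAP suggests that.

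It is also fair to say that these counts are one of several CSF displays. Section 4.9.3 summarises absolute values and changes by visit, Section 4.9.2 summarises CSF protein and leukocyte events, and Section 5.3 plans boxplots of CSF protein and leukocytes. The laboratory outputs are descriptive, with no test attached.

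All of this stands, and it limits how much the point matters. It does not rescue the rule, which is unrestricted as written and gives a wrong category whenever a result of the kinds in Step 2, or an erythrocyte result of `<1` or `<6`, occurs.

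A reader might infer more: that every censored result is misclassified, or that every below-detection erythrocyte result is wrongly called abnormal. Neither follows. Step 3 shows limits that classify correctly, and an erythrocyte result of `<2` to `<5` may truly be High. Nor does the SAP support a claim that the error favours one arm.

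**Conclusion.** The point holds as a statement that the rule can misclassify CSF safety results. For erythrocytes, `<x` can never be classed Normal for any positive x, and at `<1` and `<6` the assigned category is certainly wrong. For all four parameters, a result censored exactly at a Table 1 limit falls in a category its own inequality excludes.

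The number of patients or visits affected cannot be worked out from the SAP. It depends on the laboratory's reporting format and may be zero. The conclusion rests on the rule being applied as written, before categories are assigned, and on whole-number cell counts. It concerns descriptive safety tables and does not touch the efficacy analyses. Because the error lies in a stated rule and is cheap to remove, it should be corrected even though its frequency is unknown.

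**What to change.** Amend Section 4.9.3 so that Table 1 and shift-table categories are assigned from the reported inequality, and substitution by x is used only for descriptive statistics. In particular:

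- A result whose inequality allows only one category takes that category. Leucocytes `>5` are High, protein `<0.15` is Low, and erythrocytes `<1` are Normal.
- Where an erythrocyte result of `<x` with larger x spans more than one category, it is not counted as High or Marked High on the strength of x alone. It is shown as indeterminate.

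Treating every `<x` cell count as 0 is not recommended, because for x above 1 it would exchange possible false High results for possible false Normal ones.

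The cost is one sentence in the SAP and a small change to the program that sets the flags. An indeterminate row may appear in the CSF tables; if the laboratory reports no such results, it will be empty.

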4.9.4 Vital Signs and ECG

Absolute values and change from baseline values for vital signs and ECG data will be summarized by descriptive statistics at each visit by treatment group.

4.9.5 Columbia-Suicide Severity Rating Scale

Clinical assessments of suicidality data from CSSR-S will be summarized by descriptive statistics at each visit by treatment group.

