2.2.4 Safety Endpoints

- Incidence and severity of adverse events (AEs), with severity determined according to the Adverse Event Severity Grading Scale
- Change from baseline in Montreal Cognitive Assessment (MoCA)
- Change from baseline in vital signs
- Change from baseline in ECG parameters
- Change from baseline in clinical laboratory results
- Proportion of patients with suicidal ideation or behavior, as assessed by Columbia-Suicide Severity Rating Scale (C-SSRS) score at each visit, including

detailed focus on any individual cases identified as having severe ideation or behavior during the study conduct

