Appendix 1 Reporting Windows by Endpoints

All visits are used as labeled in the data.

Data collected at the early termination visit (for endpoints Unified Huntington's Disease Rating Scale [UHDRS], Clinical Global Impression, Change Scale [CGI-C], Patient Global Impression of Change [PGI-C], and Companion-Reported Global Impression, Change (CrGI-C): also unscheduled visits) will be mapped to the visits applying reporting windows depending on the endpoint as described in [Table 1](#).

If there are two or more assessments for an endpoint within the same visit due to the remapping of early termination or unscheduled visits, the mean of all assessments within the same visit will be considered in the analysis. If there are two or more assessments for an endpoint within the same visit but not due to the remapping of early termination or unscheduled visits, the last available assessment will be considered in the data analysis.

Table 1 Reporting Windows by Endpoints

Scheduled Week	Reporting Window (based on study day)			Reporting Window (based on study day)		
	All Endpoints except UHDRS, CGI-C, PGI-C and CrGI-C			Endpoints UHDRS, CGI-C, PGI-C and CrGI-C		
1	1	to	13	1	to	13
5	14	to	55	14	to	83
13	56	to	111			
21	112	to	167	84	to	195
29	168	to	223			
37	224	to	279	196	to	307
45	280	to	335			
53	336	to	391	308	to	419
61	392	to	447			
69	448	to	503	420	to	531
77	504	to	559			
85	560	to	615	532	to	643
93	616	to	671			
101	≥ 672			≥ 644		

CGI-C = Clinical Global Impression; Change Scale, CrGI-C = Companion-Reported Global Impression, Change; PGI-C = Patient Global Impression of Change; UHDRS = Unified Huntington's Disease Rating Scale.

Signature Page for: System identifier:RIM-CLIN-439389
Statistical Analysis Plan - BN40423 - Published

Approval Task	 Scientific content approver 12-May-2022 17:17:08 GMT+0000
---------------	--

STATISTICAL ANALYSIS PLAN

TITLE: A RANDOMIZED, MULTICENTER, DOUBLE-BLIND, PLACEBO-CONTROLLED, PHASE III CLINICAL STUDY TO EVALUATE THE EFFICACY AND SAFETY OF INTRATHECALLY ADMINISTERED RO7234292 (RG6042) IN PATIENTS WITH MANIFEST HUNTINGTON'S DISEASE

PROTOCOL NUMBER: BN40423 version 1-3

STUDY DRUG: RO7234292

VERSION NUMBER: 1

IND NUMBER: 137873

EUDRACT NUMBER: 2018-002987-14

SPONSOR: F. Hoffmann-La Roche Ltd

PLAN PREPARED BY: [REDACTED] Ph.D., [REDACTED], Ph.D.

DATE FINAL: See electronic date stamp below

STATISTICAL ANALYSIS PLAN APPROVAL

Date and Time(UTC)	Reason for Signing	Name

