- **Suicidal Ideation:** A "Yes" answer at any time post-first-dose to any one of the five suicidal ideation questions (Categories 1-5), regardless of the pre-dose responses
- **Suicidal Behavior:** A "Yes" answer at any time post-first-dose to any one of the five suicidal behavior questions (Categories 6-10), regardless of the pre-dose responses.
- **Suicidal Ideation or Behavior:** A "Yes" answer at any time post-first-dose to any one of the ten suicidal ideation or behavior questions (Categories 1-10), regardless of the pre-dose responses.
- **Treatment-Emergent Suicidal Ideation compared to recent history:** A maximum post-first-dose suicidal ideation score that is increased from the maximum suicidal ideation score in recent history.
- **Treatment-Emergent Serious Suicidal Ideation compared to recent history:** A maximum post-first-dose suicidal ideation score of 4 or 5 when the maximum suicidal ideation score during recent history was less than 4 (i.e., scores of 0-3). Only patients with a recent history score of 0-3 will be considered evaluable for this outcome.
- **Emergence of Serious Suicidal Ideation compared to recent history:** A maximum post-first-dose suicidal ideation score of 4 or 5 when the maximum suicidal ideation score during recent history was 0. Only patients with a recent history score of 0 will be considered evaluable for this outcome.
- **Improvement in Suicidal Ideation compared to baseline:** A decrease in the suicidal ideation score at the patient's week 13 (3 months), week 21 (5 months) and week 29 (7 months) C-SSRS assessment compared to the baseline score, defined as the minimum score obtained during the Screening Period (i.e., assessments collected from the Screening Visit through pre-dose on Study Day 1). Only patients with a baseline score >0 will be considered evaluable for these outcomes.

- **Emergence of Suicidal Behavior compared to all prior history:** The occurrence of suicidal behavior (a "Yes" response to one or more of Categories 6-10) post-first dose from not having suicidal behavior prior to first dose (includes the "lifetime" score collected at the Screening Visit as well as all C-SSRS assessments collected from the Screening Visit through pre-dose on Study Day 1).

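### For the main cohort, the C-SSRS is tabulated only visit by visit, with no count of patients ever affected or newly affected and no method for the promised review of severe cases

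*SAP*

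**What the plan says.** The safety endpoint in SAP Version 3 section 2.2.4 has two parts. One is a by-visit proportion: "Proportion of patients with suicidal ideation or behavior, as assessed by Columbia-Suicide Severity Rating Scale (C-SSRS) score at each visit, including". The other, in the same bullet, is a "detailed focus on any individual cases identified as having severe ideation or behavior during the study conduct".

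The analysis in section 4.9.5 is one sentence: the C-SSRS suicidality data "will be summarized by descriptive statistics at each visit by treatment group".

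On visit assignment, Appendix 1 starts from "All visits are used as labeled in the data". It maps early termination visits to scheduled weeks for all endpoints. Unscheduled visits are mapped only for UHDRS, CGI-C, PGI-C and CrGI-C: the parenthesis naming these instruments ends "Companion-Reported Global Impression, Change (CrGI-C): also unscheduled visits) will be mapped to the visits applying reporting windows". The C-SSRS is not among them.

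SAP Version 1, which covers only the 108-patient Original Design Cohort (ODC), goes further in section 3.12.5. It counts patients with a positive response to each category at any time after baseline. It defines treatment-emergent ideation as "A maximum post-first-dose suicidal ideation score that is increased from the maximum suicidal ideation score in recent history", adds serious ideation (score 4 or 5) and newly emerging behaviour, and specifies a shift table of maximum scores.

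**The concern.** Suicidal ideation can come and go. A table of percentages by visit does not say whether the same few patients are positive each time or different patients in turn. It also does not say whether a positive response is new or worse than before the first dose. The general safety baseline in section 4.9 is a single last assessment, so it does not capture ideation in the months before entry.

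The comparison between arms is what is at stake. Two arms could have near-identical by-visit tables and very different numbers of patients affected. An excess of newly affected patients on active drug could then appear only as single cases spread over many visits. Any rating made at an unscheduled visit would have no row in these tables. In addition, one part of a stated safety endpoint, the review of severe cases, has no listing, narrative or table assigned to it.

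**Working it through.** The documents give no figure for this point, so there is none to reproduce. The check has two parts.

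**Does other Version 3 text supply the missing count?**

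- Section 4.9 analyses safety overall. That pools the on- and off-treatment periods; it does not define a per-patient any-time count.
- Section 4.9.2 counts adverse events by preferred term and arm. Suicidality is not one of the selected adverse event groups, so related terms are not brought together. The summaries cover the on-treatment period; off-treatment events are listed. Adverse event terms do not reproduce C-SSRS scores or change from history.
- Section 4.9.3 gives laboratory data a shift to the minimum and maximum post-baseline value, and section 4.9.7 lists radiographic hydrocephalus cases. Section 4.9.5 has no counterpart to either.
- Version 1 section 3.12.5 has the definitions, but Version 1 states that it covers the ODC only.

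Nothing in Version 3 closes the gap.

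**What do by-visit tables leave open?**

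Inputs:

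- Patients per arm: 801 / 3 = 267 (sections 2.3 and 3.1).
- Visits: V = 13, the post-baseline weeks in the Appendix 1 table (5, 13, 21, ..., 101). That the C-SSRS was rated at all 13 is an assumption. V = 6 is shown for comparison.
- Proportion positive per visit: 1%, 2% or 3%, all assumptions. The count c is 267 times the proportion, rounded: 3, 5 or 8.
- No dropout, for simplicity.

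If c patients are positive at each of V visits, the number of distinct patients is at least c (always the same ones) and at most c × V (no patient twice). If visits were independent it would be about 267 × (1 − (1 − p)^V).

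| Per visit | V | Minimum | Maximum | If independent |
|---|---|---|---|---|
| 1% (3) | 13 | 3 (1.1%) | 39 (14.6%) | 32.7 |
| 2% (5) | 13 | 5 (1.9%) | 65 (24.3%) | 61.7 |
| 3% (8) | 13 | 8 (3.0%) | 104 (39.0%) | 87.3 |
| 3% (8) | 6 | 8 (3.0%) | 48 (18.0%) | 44.6 |

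For the 3%, 13-visit row: 8 × 13 = 104; 104 / 267 = 39.0%; 1 − 0.97^13 = 0.327; 267 × 0.327 = 87.3. The independence value is one case within the range, not its upper end. The same by-visit table is compatible with every value from 8 to 104.

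**The case against.** The best defence is that section 4.9.5 matches its endpoint. Section 2.2.4 defines a proportion at each visit, and vital signs, ECG, MoCA and safety MRI are also summarized by visit. That is correct as far as it goes: the tabulation does not contradict the by-visit part of the endpoint. It does not answer the point that the second part, on individual severe cases, has no stated method, or that the by-visit part cannot give the number of patients affected.

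Four stronger readings are tempting and are not supported:

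- A reader might infer that affected patients are never counted. They are: at each scheduled visit where they are positive, and through adverse events, serious adverse events and deaths if reported as such.
- A reader might infer that ratings made in a crisis are lost. Appendix 1 does not exclude unscheduled C-SSRS data; it gives no rule placing them in a scheduled week. The focus on severe cases in 2.2.4 is not restricted to scheduled visits. Nor do the documents show that unscheduled C-SSRS ratings were made: the main-cohort schedule is not shown, and the ODC schedule speaks of monitoring at clinic visits. Early termination ratings are already mapped.
- A reader might infer that the sponsor removed these analyses from the main-cohort plan. Version 1 was written for the ODC and announced a separate plan for the new cohort. Nothing shows that the definitions were ever planned for the main cohort.
- A reader might cite the criterion tolerating mild passive ideation at entry as evidence of risk in this cohort. It comes from the Protocol Version 3 synopsis for the ODC; the main-cohort criteria are not shown.

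**Conclusion.** The point holds in a limited form. Followed as written, Version 3 cannot report from the C-SSRS how many patients per arm ever had suicidal ideation or behaviour after the first dose, or in how many it was new or worse. Its by-visit tables have no place for any unscheduled rating, and the case review in 2.2.4 is an intention without a method.

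The size can be shown only by illustration. With 3% positive at each of 13 visits, the distinct count per arm is anywhere between 8 and 104 of 267; with 1% it is between 3 and 39. The prevalence and number of visits are assumptions. The range shows what the tables leave undetermined and says nothing about how much suicidality occurred or whether the arms differed.

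This is a cheap improvement to safety reporting. It does not show that a signal was missed.

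**What to change.** In section 4.9.5, keep the by-visit summary and add the following by arm, using all post-first-dose C-SSRS ratings including any unscheduled ones and with the definitions in Version 1 section 3.12.5:

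- any suicidal ideation and any suicidal behaviour;
- treatment-emergent ideation, and treatment-emergent serious ideation (score 4 or 5), versus recent history;
- emergent behaviour versus all prior history;
- the shift table of maximum ideation score, recent history to post-first-dose.

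Count deaths by suicide from adverse event data even where no post-dose C-SSRS exists. This needs stating because Version 1 treats patients who discontinue without a post-dose rating as unevaluable, so copying its rules unchanged could leave such a death out.

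List every patient with a post-first-dose score of 4 or 5 or any behaviour. That gives the case-level part of 2.2.4 an output.

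The cost is a few more safety tables and one listing, with definitions already written. The comparisons with history assume that the main cohort's screening C-SSRS recorded the prior 12 months and lifetime, as Version 1 describes for the ODC. If it did not, the any-time counts and the listing can still be produced, and the reference period for emergent events must be stated.

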4.9.6 Montreal Cognitive Assessment

The MoCA is an 11-item clinician-reported assessment that is used to detect cognitive impairment. It contains a series of basic assessments, including attention and visuospatial tasks. The total score ranges from 0–30, where lower scores indicate greater impairment. A scoring $\geq 26/30$ is considered normal. Individual components contributing to the total score are listed below:

- Visuospatial/executive (0 to 5)
- Naming (0 to 3)
- Attention (0 to 6)
- Language (0 to 3)
- Abstraction (0 to 2)
- Delayed recall (0 to 5)
- Orientation (0 to 6)

The total score is given by the sum of all sub scores; one point can be added for subject who has 12 years or fewer of formal education, for a possible maximum of 30 points.

Absolute values and change from baseline values for the MoCA assessment will be summarized by descriptive statistics at each visit by treatment group. The baseline for MoCA will be defined as the last assessment on Day 1.

